MM - Note: The rrMM cohort was closed to enrollment on 07-AUG-2017 due to lack of efficacy, and all subjects discontinued from treatment.

13. Has a confirmed diagnosis of active MM and measurable disease defined as:

- Serum monoclonal protein (M-protein) levels ≥ 0.5 g/dL or
- Urine monoclonal protein (M-protein) levels ≥ 200 mg/24-hrs or
- For subjects without measurable serum and urine M-protein levels, an abnormal serum free light chain ratio (FLC k/l) with involved FLC level ≥ 100 mg/L. (Normal serum FLC k/l value: 0.26-1.65).

14. Must have undergone prior treatment with ≥ 2 treatment lines of anti-myeloma therapy and must have failed their last line of treatment defined as documented disease progression during or within 60 days of completing their last anti-myeloma therapy (refractory to last line of treatment)

15. Prior anti-myeloma treatments must have included an IMiD (pomalidomide, lenalidomide, or thalidomide) AND proteasome inhibitor (bortezomib, carfilzomib, or ixazomib) alone or in combination and subject must have failed therapy with an IMiD OR proteasome inhibitor defined as one of the following:

- Refractory: Documented progressive disease on or within 60 days of completing treatment with an IMiD and/or proteasome inhibitor OR
- Relapsed and refractory: In case of prior response (\geq PR) to an IMiD or proteasome inhibitor, subjects must have relapsed within 6 months after stopping treatment with an IMiD and/or proteasome inhibitor-containing regimens.

DLBCL

16. Has a histologically confirmed diagnosis of DLBCL.

17. Subjects must have progressed following at least 2 lines of previous therapy, including progression after an autologous stem cell transplant (SCT), or are not a candidate (per institutional criteria) for an autologous stem cell transplant. Subjects who are ineligible for standard treatment or who have withdrawn from standard treatment due to unacceptable toxicity warranting discontinuation of that treatment and precluding retreatment with the same agent before progression of disease will also be eligible.

18. Have measurable disease, defined as at least one lesion that can be accurately measured in at least 2 dimensions with spiral computed tomography (CT) scan. Minimum measurement must be > 15 mm in the longest diameter or > 10 mm in the short axis.

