10. Has active autoimmune disease that has required systemic treatment in past 2 years (ie, with use of disease modifying agents, corticosteroids or immunosuppressive drugs). Replacement therapy (eg, thyroxine, insulin, or physiologic corticosteroid replacement

therapy for adrenal or pituitary insufficiency, etc.) is not considered a form of systemic treatment and is allowed.

11. Has a history of (non-infectious) pneumonitis that required steroids or current pneumonitis.
12. Has an active infection requiring intravenous systemic therapy.
13. Has known psychiatric or substance abuse disorders that would interfere with cooperation with the requirements of the trial.
14. Is pregnant or breastfeeding, or expecting to conceive or father children within the projected duration of the trial, starting with the pre-screening or screening visit through 120 days after the last dose of trial treatment.
15. Has received prior therapy with an anti-PD-1, anti-PD-L1, anti-PD-L2 anti-CD137, or anti-CTLA-4 antibody (including ipilimumab or any other antibody or drug specifically targeting T-cell co-stimulation or checkpoint pathways) or CAR-T cell therapy or with an agent directed to another stimulatory or co-inhibitory T-cell receptor.
16. Previously treated with a CDK inhibitor (eg, dinaciclib or flavopiridol).
17. Has a known history of human immunodeficiency virus (HIV) infection. No HIV testing is required unless mandated by local health authority.
18. Has a known history of or is positive for hepatitis B (hepatitis B surface antigen [HBsAg] reactive) or hepatitis C (hepatitis C virus [HCV] RNA [qualitative] is detected).
19. Has received a live vaccine within 30 days prior to first dose.
20. Has known current symptomatic congestive heart failure, unstable angina pectoris, or cardiac arrhythmia.

CLL

21. Subject with Richter's Transformation.

MM

22. Subjects with non-secretory or oligo-secretory myeloma, plasma cell leukemia, or Waldenström's macroglobulinemia.
23. History of primary amyloidosis, hyperviscosity or POEMS syndrome (plasma cell dyscrasia with polyneuropathy, organomegaly, endocrinopathy, monoclonal protein, and skin changes).

DLBCL

24. Subjects with primary mediastinal B-cell lymphoma.
25. Subject with Richter's Transformation.

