- m. For subjects with CLL and DLBCL who will receive rasburicase as a premedication, G6PD testing should be completed locally when required in subjects at higher risk of G6PD deficiency (eg, subjects of African or Mediterranean ancestry). These subjects should be tested and found to have adequate levels before treatment with rasburicase (Section 5.2.1.3.1).
- n. All subjects must provide newly obtained (within 3 months) bone marrow biopsy material for biomarker analysis at screening. If bone marrow biopsy was performed within 3 months before screening but subject had anticancer treatment after biopsy, the bone marrow biopsy and aspiration should be repeated. If bone marrow biopsy was performed within 3 months before screening but subject has not had anticancer treatment after biopsy, the bone marrow biopsy and aspiration does not need to be repeated. Subjects with rrDLBCL must provide core or excision biopsy of a lymph node or extranodal lesion (performed within 3 months) at screening. For MM, bone marrow analysis will include bone marrow morphology, IHC, Cytogenetics by standard karyotyping, FISH panel. Post-baseline bone marrow or lymph node (DLBCL) assessments should be performed to confirm response as defined by disease-specific criteria, or as clinically indicated. For DLBCL, subsequent bone marrow assessment will only be performed in subjects who have bone marrow involvement at screening. A bone marrow biopsy assessment should be performed to confirm CR (if subject had bone marrow involvement at screening) and as clinically indicated.
- o. Baseline serum and urine M protein (24 hr) levels will be assessed by electrophoresis and immunofixation. Free light chain (FLC) levels and ratio will also be assessed. If serum M protein by electrophoresis (SPEP) is ≥ 1 g/dL at baseline, SPEP will be assessed after each cycle. Post-baseline serum: immunofixation needed only in absence of M-spike. Post-baseline: perform all serum, urine, and FLC analyses as needed to confirm response per criteria.
- p. If baseline urine M protein (24 hr) by electrophoresis (UPEP) ≥ 200 mg, collect urine (24 hr) after each cycle. Otherwise, assess urine protein (24 hr) as needed to confirm response per criteria.
- q. FLC post-baseline: for subjects with non-secretory myeloma (SPEP < 1 g/dL and UPEP < 200 mg/24 hr) at baseline, but serum light chain ≥ 10 mg/dL, serum FLC will be assessed after each cycle. Otherwise, assess FLC as needed to confirm response per criteria.

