7.1.2.8 Assessment of Disease and Tumor Response

7.1.2.8.1 CLL Response Assessments

Disease assessments or scans performed as part of routine clinical management are acceptable for use as the screening scan if they are of diagnostic quality and performed within 28 days prior to Cycle 1 Day 1.

CT scans of the neck, chest, abdomen, and pelvis will be obtained at screening within 28 days of Cycle 1 Day 1. Follow-up CT scans of the neck should be performed if enlarged lymph nodes (defined as ≥ 1.5 cm) are detected on the screening CT neck scan or if medically indicated by the discretion of the treating physician.

CT scans will be repeated every 3 cycles (approximately 9 weeks) despite any delays in treatment. CT scans will be read locally.

Response will be determined locally according to the iwCLL criteria, using results of the subject's CT scan, hematology laboratory results (complete blood counts), and presence of CLL symptoms as described in Section 12.7. Response assessments should be completed in conjunction with the subject's CT scan schedule.

If medically appropriate, a confirmatory assessment of the initial progression event should be performed within 9 weeks. A CT scan of the neck (if indicated), chest, abdomen and pelvis and hematology laboratory (complete blood counts) will be obtained, and the presence of CLL symptoms will be determined at each response assessment time point.

7.1.2.8.2 Multiple Myeloma Response Assessments:

7.1.2.8.2.1 Myeloma Laboratory Testing Disease Measurements

Baseline

For subjects with MM, collect serum and urine samples within 28 days of Cycle 1 Day 1 for baseline disease assessment. Baseline serum and urine (24 hr) M protein levels will be assessed by electrophoresis and immunofixation. Free light chain (FLC) levels and ratio will also be assessed.

Serum electrophoresis (SPEP)

If serum M protein by electrophoresis (SPEP) ≥ 1 g/dL at baseline, SPEP will be assessed after each cycle.

Urine electrophoresis (UPEP)

If urine M protein (24 hr) by electrophoresis (UPEP) ≥ 200 mg, UPEP (24 hr) will be assessed after each cycle.

FLC

For subjects with non-secretory myeloma (SPEP < 1 g/dL and UPEP < 200 mg/24 hr) at baseline, but serum light chain ≥ 10 mg/dl, serum FLC will be assessed after each cycle.

Best Response

Laboratory assessments should be repeated to confirm best response, including SPEP and UPEP, serum and urine immunofixation, and FLC. Bone marrow biopsy is recommended to confirm CR.

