8.6.4 Overall Survival

The median OS, if reached, will be estimated in the given analysis population. In addition, the Kaplan-Meier method will be used to estimate the survival curve.

Table 19 Analysis Methods for Efficacy Endpoints (Signal Detection)

Endpoint/Variable	Statistical Method	Analysis Population	Missing Data Approach
Primary:			
ORR – by investigator assessment using disease-specific criteria ^a	2-sided 95% exact confidence interval	ASaT	Subjects with missing data are considered non-responders.
Secondary:			
DOR – by investigator assessment using disease-specific criteria ^a	Summary statistics using Kaplan-Meier method	All responders	Non-responders are excluded in analysis.
PFS – by investigator assessment using disease-specific criteria ^a	Summary statistics using Kaplan-Meier method	ASaT	Censored at last assessment (see Table 18 for additional details)
OS	Summary statistics using Kaplan-Meier method	ASaT	Censored at last assessment
^a CLL based on iwCLL guidelines [1]; MM based on IMWG criteria [2]; DLBCL based on the Revised Response Criteria for Malignant Lymphoma [3]. Abbreviations: ASaT = all subjects as treated; DOR = duration of response; ORR = objective response rate; OS = overall survival; PFS = progression-free survival.			

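### The myeloma sections disagree on which marker is followed: under the flow chart footnotes, a subject with serum M-protein of 0.5 to <1 g/dL can meet inclusion 13 yet trigger no per-cycle test

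*Combined protocol and SAP*

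**What the plan says.** **Eligibility.** Inclusion 13 (Section 5.1.2) defines measurable myeloma by any one of three routes: "Serum monoclonal protein (M-protein) levels ≥ 0.5 g/dL or" "Urine monoclonal protein (M-protein) levels ≥ 200 mg/24-hrs or", for subjects measurable in neither serum nor urine, "an abnormal serum free light chain ratio (FLC k/l) with involved FLC level ≥ 100 mg/L". Exclusion 22 (Section 5.1.3) bars "Subjects with non-secretory or oligo-secretory myeloma" and defines neither term.

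**Per-cycle testing, footnotes and text.** Footnote o of the flow chart (Section 6.0) states that, if serum M-protein by electrophoresis (SPEP) is at least 1 g/dL "at baseline, SPEP will be assessed after each cycle". Footnote p sets the urine (UPEP) trigger at 200 mg. Footnote q requires FLC each cycle only when SPEP is below 1 g/dL, UPEP is below 200 mg/24 h and light chain is at least 10 mg/dL, and it labels that SPEP/UPEP combination non-secretory. Section 7.1.2.8.2.1 repeats the three triggers. Outside them, the footnotes leave testing to be done when needed to confirm a response.

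**Per-cycle testing, grid.** The grid marks SPEP, UPEP and FLC at screening, Cycle 2 Day 1, Cycle 3+ Day 1 and discontinuation. Footnote i requires a disease assessment at the start of every cycle from Cycle 2 for all myeloma subjects, with no M-protein threshold.

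**Analysis.** For ORR in the ASaT population, Table 19 states: "Subjects with missing data are considered non-responders". The futility set in Section 8.7 is the first 12 subjects who were treated and have at least one post-baseline disease assessment. The myeloma cohort may stop at 0 responses in 12.

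**The concern.** The value that makes a subject measurable at entry should be the value followed for response. Here the serum threshold for entry is half the threshold that triggers serial serum testing, and neither of the other two triggers is certain to cover the difference.

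The response criteria in Section 12.8 make this matter. Partial response needs a fall of at least 50% in serum M-protein, every response category needs two consecutive assessments, and biochemical progression is judged on a rise from baseline. Testing only when a response needs confirming is circular for a subject whose serum marker is not otherwise measured, because the response must be suspected first. Other sources are thin: immunoglobulin quantification is marked at screening only, and marrow and imaging are done as needed.

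At stake is how the myeloma ORR is read. A subject whose marker was not followed and a subject whose disease did not respond look the same in the ASaT result. One unseen response also matters for a rule set at 0/12.

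**Working it through.** **1. The plan's own figure.** Section 8.7 says that 0/12 rules out an ORR of 17% with one-sided 90% confidence. The exact upper limit is 1 − 0.10^(1/12) = 17.46%. At exactly 17%, P(0/12) = 0.83^12 = 10.7%. The stated figure is reproduced to rounding.

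**2. Who meets inclusion 13 but no trigger.** The light chain units agree: 100 mg/L = 10 mg/dL. Crossing the three baseline markers against inclusion 13 and footnotes o to q gives:

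| Baseline SPEP (g/dL) | UPEP (mg/24 h) | FLC (mg/dL) | Meets inclusion 13 | Triggered each cycle |
|---|---|---|---|---|
| <0.5 | <200 | <10 | no | – |
| <0.5 | <200 | ≥10 | yes (if ratio abnormal) | FLC |
| <0.5 | ≥200 | any | yes | UPEP |
| 0.5 to <1 | <200 | <10 | **yes** | **none** |
| 0.5 to <1 | <200 | ≥10 | yes | FLC |
| 0.5 to <1 | ≥200 | any | yes | UPEP |
| ≥1 | <200 | any | yes | SPEP |
| ≥1 | ≥200 | any | yes | SPEP, UPEP |

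Exactly one combination falls through, and it needs all three conditions together.

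**3. What else the documents say about that combination.**

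- Grid and footnote i: all three tests and an assessment every cycle, so no gap.
- Footnotes o to q and Section 7.1.2.8.2.1: no test each cycle, so a gap.
- Footnote q with exclusion 22: SPEP <1 g/dL with UPEP <200 mg/24 h is non-secretory, so the subject is excluded.
- Inclusion 13: the subject is admitted.

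These cannot all hold.

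**4. Route into the analyses.** In the ASaT ORR, a treated subject with missing response data is a non-responder. In the futility set, a subject with no post-baseline assessment is not among the 12. A gap subject counts there only if an assessment was recorded without the relevant marker, which footnote i makes possible.

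**5. Size, worst case.** Let f be the share of subjects in the gap. The documents do not give f, so the values below are assumptions. Assume also that every gap response is missed and, for the futility column, that gap subjects enter the 12 as just described. Then observed ORR = true ORR × (1 − f), and P(0/12) = (1 − observed ORR)^12.

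| f | Observed ORR, true 20% | P(0/12) | Observed ORR, true 30% | P(0/12) |
|---|---|---|---|---|
| 0 | 20% | 0.80^12 = 6.9% | 30% | 0.70^12 = 1.4% |
| 5% | 19% | 0.81^12 = 8.0% | 28.5% | 0.715^12 = 1.8% |
| 10% | 18% | 0.82^12 = 9.2% | 27% | 0.73^12 = 2.3% |
| 20% | 16% | 0.84^12 = 12.3% | 24% | 0.76^12 = 3.7% |

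With 30 subjects and a true ORR of 30%, expected observed responders fall from 9.0 to 30 × 0.24 = 7.2 at f = 20%. With the SPEP trigger at 0.5 g/dL, the gap is empty and the f = 0 row applies.

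**The case against.** The strongest reply is that the plan does schedule the tests. The grid marks all three markers every cycle, footnote i requires an assessment every cycle, and no text says that the footnotes override the grid. This stands to the extent that the documents conflict; they do not plainly omit the test. It does not remove the problem. The rows in question carry footnotes o to q, whose fallback clauses have no purpose if everyone is tested every cycle, and the detailed text in Section 7.1.2.8.2.1 restates the thresholds. A site could reasonably follow either.

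Second, the as-needed clause and the repeat testing at best response (Section 7.1.2.8.2.1) mean that response is not undetectable in this group. That is correct: missed responses are a possibility, not a certainty.

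Third, on footnote q's label the whole group is excluded and has size zero. That may be so, but inclusion 13 says otherwise. Section 12.8 does not settle it either: its pointer to a Table 4 for measurable disease leads to a table that is not reproduced, and the protocol's own Table 4 concerns immune-related events.

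Fourth, enrollment closed on 07-AUG-2017 and all myeloma subjects stopped treatment, so a new schedule helps no one. This is right, and it limits the practical remedy to reporting.

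A reader might also infer that Table 19 puts these subjects into the futility count as non-responders, or that the gap contributed to closure for lack of efficacy. The documents support neither. Table 19 governs the ASaT ORR, and Section 8.7 has its own evaluability condition. No passage gives the number of gap subjects or links marker testing to the closure.

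**Conclusion.** The inconsistency is real and appears in several places: inclusion 13 against footnotes o to q and Section 7.1.2.8.2.1, those footnotes against the grid and footnote i, and inclusion 13 against exclusion 22 as footnote q would have it read. Under the footnote reading, one defined subgroup has no per-cycle marker. Under the grid reading, none does.

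The effect on ORR cannot be derived from the documents. It is nil if no such subjects enrolled, or if sites tested every cycle. The figures at shares of 5% to 20% are an upper bound for each assumed share, because they take every gap response as missed. Even then the shift is moderate: at a true ORR of 20%, the chance of 0/12 rises by at most 12.3 − 6.9 = 5.4 percentage points. The point is worth acting on because the check is cheap and separates unassessed subjects from true non-responders in a cohort reported as stopped for lack of efficacy.

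**What to change.** **Text.** Reconcile inclusion 13, exclusion 22, the grid, footnotes i and o to q, and Section 7.1.2.8.2.1 so that the marker that qualified a subject is the one measured each cycle. Either set the SPEP trigger at the inclusion threshold or require SPEP every cycle as the grid shows. Define non-secretory and oligo-secretory so that exclusion 22 and inclusion 13 cannot both apply to one subject.

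**Closed cohort.** Through the supplemental statistical analysis plan that Section 8.0 provides for before database lock:

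1. Count the myeloma subjects with baseline SPEP 0.5 to <1 g/dL, UPEP <200 mg/24 h and FLC <10 mg/dL.
2. State for each whether the qualifying marker was measured each cycle.
3. Report ORR in subjects whose marker was actually measured, as a supporting line beside the ASaT ORR.

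The third item also drops subjects who lack serial values for other reasons, such as early discontinuation, so it may read higher than the ASaT figure and should not replace it. If the count is zero, one sentence closes the matter.

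**Cost.** Wording changes, one tabulation from baseline and laboratory data, and one extra ORR line. No new data collection is needed.

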7.0 TRIAL PROCEDURES

7.1 Trial Procedures

The Trial Flow Chart - Section 6.0 summarizes the trial procedures to be performed at each visit. Individual trial procedures are described in detail below. It may be necessary to perform these procedures at unscheduled time points if deemed clinically necessary by the investigator.

Furthermore, additional evaluations/testing may be deemed necessary by the investigator and or the Sponsor for reasons related to subject safety. In some cases, such evaluation/testing may be potentially sensitive in nature (e.g., HIV, Hepatitis C, etc.), and thus local regulations may require that additional informed consent be obtained from the subject. In these cases, such evaluations/testing will be performed in accordance with those regulations.

7.1.1 Administrative Procedures

7.1.1.1 Informed Consent

The investigator or qualified designee must obtain documented consent from each potential subject or each subject's legally acceptable representative prior to participating in a clinical trial or Future Biomedical Research.

7.1.1.1.1 General Informed Consent

Consent must be documented by the subject's dated signature or by the subject's legally acceptable representative's dated signature on a consent form along with the dated signature of the person conducting the consent discussion.

A copy of the signed and dated consent form should be given to the subject before participation in the trial.

The initial informed consent form, any subsequent revised written informed consent form and any written information provided to the subject must receive the IRB/ERC's approval/favorable opinion in advance of use. The subject or his/her legally acceptable representative should be informed in a timely manner if new information becomes available that may be relevant to the subject's willingness to continue participation in the trial. The communication of this information will be provided and documented via a revised consent form or addendum to the original consent form that captures the subject's dated signature or by the subject's legally acceptable representative's dated signature.

Specifics about a trial and the trial population will be added to the consent form template at the protocol level.

The informed consent will adhere to IRB/ERC requirements, applicable laws and regulations and Sponsor requirements.

7.1.1.1.2 Consent and Collection of Specimens for Future Biomedical Research

The investigator or qualified designee will explain the Future Biomedical Research consent to the subject, answer all of his/her questions, and obtain written informed consent before

performing any procedure related to Future Biomedical Research. A copy of the informed consent will be given to the subject.

7.1.1.2 Inclusion/Exclusion Criteria

All inclusion and exclusion criteria will be reviewed by the investigator or qualified designee to ensure that the subject qualifies for the trial.

7.1.1.3 Subject Identification Card

All subjects will be given a Subject Identification Card identifying them as participants in a research trial. The card will contain trial site contact information (including direct telephone numbers) to be utilized in the event of an emergency. The investigator or qualified designee will provide the subject with a Subject Identification Card immediately after the subject provides written informed consent.

The subject identification card also contains contact information for the emergency unblinding call center so that a health care provider can obtain information about trial medication/vaccination in emergency situations where the investigator is not available.

